112 from Western studies cannot be assumed, since the eventual results of implementation are
113 dependent on the context and culture that the health system is situated within. Current evidence on
114 the effectiveness of these interventions programme is moreover mixed (17, 22), with little insight
115 into whether the programme logic or the delivery process needs to be adjusted. Better
116 understanding of the conditions of implementation would support practitioners and policymakers
117 to consider how to ensure complex interventions achieve their intended impact. Hence, the
118 specificity of cultural context in the unique healthcare system of Singapore and the lack of
119 understanding of stakeholder perceptions warrant a comprehensive evaluation of the GSH model.
120 In the next segment, we will briefly describe the GSH programme and its position in Singapore's
121 healthcare system.

122 **Geriatric Services Hubs**

123 The Singapore Healthcare System consists of three regional healthcare systems (RHS) in the
124 central, eastern, and western regions of Singapore. These RHS were established to coordinate and
125 organise healthcare service providers, integrate care across providers, and manage population
126 health for their respective regions. Hence, each RHS consists of a network led by a major public
127 hospital in collaboration with other healthcare providers such as primary care, day rehabilitation,
128 and community hospitals within the same geographical region (30). Each RHS is provided with
129 funding to implement programmes to deliver comprehensive care beyond the hospital to the
130 community. However, fragmentation in healthcare delivery continues to exist between and within
131 each RHS. There are other forms of commonly utilised care services that are privately owned and
132 not under the jurisdiction of the RHS, which include daycare, day rehabilitation centres, private
133 clinics and other variations of healthcare and allied health services. Therefore, although
134 geographically located within the same region, differences in governance and financing structures
135 between the RHS funded services and privately-owned facilities result in insufficient information
136 transfer, in capabilities and capacities between healthcare providers, and acute hospital-centricity.

137 Currently, as part of a national effort to engage and support older adults in Singapore,

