To assess the process of development and implementation of the new programme	
• To examine the perceptions, roles, responsibilities, and experience in developing and implementing each programme• To understand the workflow from the perspective of each profession for each of the new programmes• To improve competency of primary care providers in identifying, caring and managing geriatric patients in the community• To explore differences in contextual factors across the five sites that have influenced implementation experiences and outcomes• To understand care recipients' experiences in receiving frailty care in the community	Qualitative - Semi-structured in-depth interview with key policy and programme decision-makers Qualitative - Semi-structured focus group discussions with health and social care professionals and care recipients Qualitative – Participant observations Quantitative – Longitudinal monitoring of process indicators
To assess the health, quality of life, and user experience effects on care recipients and the burden of care on primary caregivers	
• To compare outcomes between baseline, 3- and 6-months for each programme	Quantitative - Pre-test post-test design using survey-based data collection
To determine the impact on healthcare utilisation and cost impact of the new programme	
• To assess the use of healthcare services and costs between participants and non-participants for each programme	Quantitative - Retrospective cohort design with propensity score matched comparators

208
209 Based on the components the sites are funded for (Table 1), we will evaluate the GSH
210 program conducted by Ng Teng Fong General Hospital (NTFGH) based on evaluation objective 1
211 – to assess the process of development and implementation of the new programme. The focus is
212 on competency building, with the funding being utilised to cover the time spent by trainers and
213 trainees. In addition, the funding will not be used to cover healthcare costs incurred by patients.

214 Based on these considerations, evaluation objectives 2 and 3 would not be representative of the
215 results of the program. The remaining four sites will be evaluated on all three evaluation objectives
216 as their funding structures includes subsidising the healthcare costs of patients.

217 **Qualitative Evaluation**

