- 354 1. GSH sites offer a range of medical, social and other services through either direct provision
355 or referrals. Given that the model is intended to bridge service gaps (conduct of CGA in
356 the community), in the short-term, we hypothesis **an increase in the utilisation of**
357 **appropriate services** (rehabilitation, ambulatory services) in this time-limited programme.
- 358 2. GSH participants are expected to benefit from the comprehensive package of health and
359 social services and multidisciplinary team approach. With **better care coordination and**
360 **improved access**, it is likely to elicit a **higher level of satisfaction** relative to comparator
361 groups.
- 362 3. Education of the client about self-care and making decisions about potential care options
363 with inputs from a multidisciplinary team is expected to result in **higher level of shared**
364 **decision making** and **engagement** relative to comparator groups.
- 365 4. It is hypothesised to result in **better functional status and health outcomes**, **might reduce**
366 **the healthcare utilisation** (emergency hospitalisation, nursing home admission),
367 **caregiver burden** and **the associated indirect cost**. In turn, we might expect **overall costs**
368 **to be lower** compared to the comparison group.

369 An interviewer-administered survey will be conducted to collect data on demographic and

370 baseline health status, and data measuring the impact of the programme on patient activation, user

371 experience and satisfaction with care, health status, quality of life, the burden of care on primary

372 caregivers, and health utilisation and cost. The data are collected at baseline, 3-months and 6-

373 months (Table 5). After obtaining informed consent, participants will be asked to complete a

374 survey estimated to take about 45 to 90 minutes. Participants will complete the survey up to three

375 time-points – baseline (within 1 month of programme enrollment) and at 3-months and 6-months.
376 The primary caregiver will also be asked to complete a 5 to 10-minute survey at the same three
377 time points on caregiver burden. In the event a participant is clinically certified to have dementia,
378 we will allow a proxy respondent to answer on behalf of the main participant. Participants will
379 receive a token of appreciation for their involvement in the study.

380 Table 5. List of indicators for measuring programme impacts

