Impact outcomes	Assessment	Measure
Patient engagement		
Shared decision making	collaboRATE For Patient – 5-point anchor scale	Patient's experience of shared decision making
Patient activation	13-item Patient Activation Measure (PAM-13)	Level of patient activation, including ability to self-manage, maintain functioning, collaborate with healthcare providers, and access healthcare services
Healthcare experiences		
Experience of care delivered	Consumer Assessment of Healthcare Providers and System Clinician & Group Survey Version 3.0 (CG-CAHPS)	Patients' experience with healthcare providers and staff in doctors' offices
Health status, adverse outcomes and quality of life		
Functional status	Barthel Index of Activities of Daily Living (ADL)	Functional independence in ADL such as feeding, bathing, and continence
Frequency of falls	Count of falls	Marker of poor health and declining function
Health-related quality of life	EuroQol-5D-5L	Health-related quality of life in domains including mobility, self-care, usual activities, pain, anxiety and depression
	19-item Quality of Life Scale (CASP-19)	Quality of life in later life in domains including control, autonomy, self-realisation, and pleasure
Impact on caregivers		
Level of caregiver burden	Zarit Burden Interview (ZBI)	Level of burden experienced by primary caregivers of older adults with dementia
Direct and indirect cost		
Societal cost	Client Service Receipt Inventory (CSRI)	Health, social and informal care use and cost

381
382 To compare the healthcare utilisation and cost between programme enrollees and a
383 comparator group, an anonymised analytical dataset comprising existing information drawn from
384 datasets maintained by each of the five GSH sites, the evaluation team and the Ministry of Health

385 will be established. Given that all persons residing lawfully in Singapore are issued a unique
386 National Registration Identity Card (NRIC) number by the government, the NRIC for each
387 enrollee will be assigned a unique identifier by a third party. This unique identifier will
388 subsequently be used to merge data across the datasets. The anonymised data set will comprise
389 sociodemographic variables, all information collected from the above survey, and information on
390 the use and system cost of healthcare services (primary care, specialist care, emergency services,
391 inpatient care) across all public healthcare institutions in Singapore as well as mortality data.

392 **Data Analysis**

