446 corroboration. Qualitative findings could offer explanations for the effectiveness of the GSH in
447 terms of the impacts on health status, quality of life, user experience, and healthcare resource use
448 and costs.

449 **Discussion**

450 The purpose of the GSH programme is to provide comprehensive and coordinated care for
451 frail older adults in the community, and the programme aims to achieve this through collaborative
452 working arrangements with various health and social service providers in the community. The
453 suite of services provided includes conducting CGA to identify the needs of older adults, and to

454 increase accessibility of frail older adults to essential services. Five GSH pilot sites share these
455 common goals but due to differences in their innate organisational operations, the design of the
456 GSH model was different to harness their existing relationships and organisational strengths.

457 The motivation to conduct a multiple methods evaluation is driven by the need to provide
458 good quality evidence on the organisation of community-based frailty care. Integration between
459 acute care and other forms of care in the community is becoming increasingly advocated (61). As
460 GSH is a model of care that aims to provide comprehensive care to frail older adults, it is essential
461 to gain rich insights into the development and implementation of the programme. The
462 understanding of underlying mechanisms will help us determine each programme's effects on
463 patients' health outcomes, programme cost-effectiveness, and the programme replicability.
464 Variations in the operations at each site demands that our evaluation methods be rigorous and
465 consistent across all sites. This will enable us to identify essential links in each model and
466 contribute more effectively to the planning of future models that provide comprehensive care.

467 **Strengths and limitations**

468 The study protocol has several strengths. Firstly, the multiple method approach allows in-
469 depth understanding of the programme from the point of view of different stakeholders, as well as
470 the programme's attributed health outcomes and costs impact. Secondly, this approach also
471 enables us to triangulate our findings, and cross compare the validity and reliability of our findings
472 through the different mediums of data collection. Finally, the choice of propensity score to match

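### The between-group cost comparison covers only listed public-sector services, so it cannot test the hypotheses on overall cost and nursing home admission or support a cost-effectiveness statement

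*Combined protocol and SAP*

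**What the plan says.** Under Study Procedure, Quantitative Evaluation (after Table 5), the dataset for the utilisation and cost comparison is to hold "sociodemographic variables, all information collected from the above survey, and information on" "the use and system cost of healthcare services (primary care, specialist care, emergency services", ending "inpatient care) across all public healthcare institutions in Singapore as well as mortality data".

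The survey part includes the CSRI, which Table 5 describes as "Health, social and informal care use and cost", and the EuroQol questionnaire. The Evaluation Design describes the survey as a single cohort of enrollees without a parallel control group. The Study Sample section takes comparators from an existing Ministry of Health dataset and describes no survey of them.

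Hypothesis 4 says that the programme might reduce healthcare use ("emergency hospitalisation, nursing home admission"), caregiver burden and indirect cost, and that overall cost might then be lower than in the comparison group. The Discussion says that understanding the mechanisms will help to determine each programme's effects on health outcomes, "programme cost-effectiveness, and the programme replicability".

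The text after Table 2 keeps four sites in objectives 2 and 3 "as their funding structures includes subsidising the healthcare costs of patients". The section on the Geriatric Services Hubs describes commonly used, privately owned services as "not under the jurisdiction of the RHS, which include daycare, day rehabilitation centres, private" clinics among others. In Table 1, two of those four sites deliver partly in private general practice. Data Analysis plans a generalised linear model for cost, with results given as ratios.

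**The concern.** The cost hypothesis is broader than the cost data available in both groups. It speaks of overall cost and reaches that through indirect cost and nursing home admission, while the items listed for both groups are four types of care at public institutions.

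The programme is also meant to change where care is given. Hypothesis 1 expects more rehabilitation and ambulatory care, and hypothesis 4 expects fewer emergency hospitalisations. Emergency and inpatient care are on the list, but rehabilitation is not a named cost category. Programme delivery is a cost that only enrollees can incur, and it is not a listed item either.

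At stake is how objective 3 is read. A ratio below 1 could be reported to the funder as lower overall cost when it shows only lower cost in the measured services. The Strengths and limitations section credits matching with supporting the validity of the cost conclusions, but matching addresses confounding and cannot supply costs that were not recorded. The limitations do not mention the scope of the cost data.

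**Working it through.** The plan states no cost figure, so there is nothing to reproduce. The check has two parts.

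**1. What is listed for each group.**

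| Item | Enrollees | Comparators |
|---|---|---|
| Primary, specialist, emergency and inpatient care, public institutions | Listed | Listed |
| Mortality | Listed | Listed |
| Health, social and informal care (CSRI) | Survey participants only | None described |
| EuroQol | Survey participants only | None described |
| Nursing home admission | Not listed as a separate item | Not listed |
| Care from private providers | Only as far as the CSRI captures it | Not listed |
| Programme delivery cost | Not listed | Does not arise |

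The first two rows can be contrasted between groups. The CSRI and EuroQol rows support a pre-post description in enrollees. On the listed contents, nursing home admission cannot be compared. A cost-effectiveness result needs incremental cost and incremental effect; the EuroQol is not described for comparators, and Data Analysis states no cost perspective, quality-adjusted life-years or incremental ratio.

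**2. What omitted cost could do (assumed values only).** Set the comparators' mean recorded public cost to 1. Let *r* be the relative saving in recorded cost among enrollees, *c* the comparators' unrecorded cost, and *u* the enrollees' unrecorded cost minus *c*, including programme cost not already in system cost.

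- Observed ratio = 1 − *r*
- Full ratio = (1 − *r* + *c* + *u*) / (1 + *c*)

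With *r* = 0.10 the observed ratio is 0.90 throughout:

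| *c* | *u* | Full ratio |
|---|---|---|
| 0 | 0.05 | 0.95 / 1 = 0.95 |
| 0 | 0.10 | 1.00 / 1 = 1.00 |
| 0 | 0.20 | 1.10 / 1 = 1.10 |
| 0.20 | 0.10 | 1.20 / 1.20 = 1.00 |
| 0.20 | 0.20 | 1.30 / 1.20 = 1.08 |
| 0.20 | −0.10 | 1.00 / 1.20 = 0.83 |

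The full ratio equals 1 when *u* = *r*, whatever *c* is. An apparent saving of 5%, 10% or 20% therefore disappears once the extra unrecorded cost in enrollees reaches 5%, 10% or 20% of the comparators' recorded cost. If enrollees use less unrecorded care, for example through fewer nursing home stays, the observed ratio understates the saving (last row).

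A ratio alone cannot be set against programme cost. With comparator mean *M*, the saving per person is *M* × (1 − ratio), and programme cost per enrollee is subtracted from that amount.

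**The case against.** The strongest reply is that the plan claims little. Lower cost is worded as something that might be expected, cost-effectiveness appears once in the Discussion and is not an objective, and objective 3 speaks only of healthcare utilisation and cost impact. That is correct, and it makes this a mismatch between a hypothesis and its data. It does not remove the mismatch, because hypothesis 4 names the comparison group for overall cost.

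A reader might infer more, in four ways that the documents do not support:

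- **That all cost data are limited to public institutions.** The same sentence brings the survey, and so the CSRI, into the dataset. The gap lies in the between-group contrast.
- **That programme cost is certainly left out.** The site and Ministry datasets are not itemised and the term system cost is not defined, so the omission is inferred from the listed contents. A subsidy changes who pays; some subsidised care may already be counted, and adding grant cost without a check could count it twice.
- **That day rehabilitation lies wholly outside the public networks.** The plan also lists day rehabilitation and community hospitals within each regional system; only the privately owned services are outside. Delivery at the two sites concerned is mixed, private and public.
- **That omitted cost falls mainly on enrollees, so the bias favours the programme.** Comparators can use private clinics and daycare too, and fewer nursing home admissions would be an unmeasured saving.

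Hypothesis 1 on rehabilitation names no comparator and can be examined within enrollees, so it need not change.

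**Conclusion.** The point holds for the between-group comparison. As written, the plan would test a hypothesis about overall cost on a partial set of costs, could not compare nursing home admission on the data listed, and mentions cost-effectiveness without an analysis to support it. Cost shifting could appear as a saving, and a real saving could be hidden. Neither the direction nor the size can be determined from the documents; the range of 0.83 to 1.10 around an observed 0.90 only illustrates the assumed inputs.

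The conclusion rests on two readings: that the listed contents of the dataset are complete, and that no survey of comparators is planned. If the Ministry data hold nursing home admissions for both groups, that part falls away.

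**What to change.** 1. Restate the between-group part of hypothesis 4 and objective 3 as utilisation and cost of public-sector primary, specialist, emergency and inpatient care. Remove nursing home admission from the between-group hypothesis unless the Ministry data hold it for both groups.
2. Report the adjusted mean cost difference per person beside the ratio. Set it against the funded programme cost per enrollee at each of the four sites, excluding subsidised care already counted in system cost.
3. Report wider care from the CSRI as a pre-post description in enrollees only.
4. Drop the reference to cost-effectiveness from the Discussion.

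Items 1, 3 and 4 are changes of wording and reporting. Item 2 needs a programme cost figure from each of the four sites, some allocation of shared cost such as set-up and training, and a check for double counting. No new participant data are needed. The price is a narrower cost conclusion.

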246 desired outcomes. We will monitor quantitative process outcomes longitudinally on a quarterly
247 basis over the three-year pilot timeframe to assess the level of receptivity towards the new
248 programme, partner organisations' ability to accurately screen for frailty, provision of personalised
249 and goal-oriented care, and care-continuity.

250 Second, a single cohort, pre-test post-test design (pre-experimental design) will be used to
251 quantify the impact of participation in the programme on care recipient-reported health outcomes,
252 experience of care, and caregiver's burden. There will be no randomised parallel control group
253 due to programmes' reluctance, as they expect high refusal rates from patients. In addition, the
254 new model encompasses different care components tailored to each patient's needs, which renders
255 it impractical to conduct a 'true' experimental design with randomisation and a separate control
256 group (44).

257 Third, a retrospective pre-post, matched-groups design will be implemented to compare
258 healthcare utilisation and cost. Due to the absence of a parallel control group, we have opted for a

259 quasi-experimental design to determine the cost impact of introducing the new programme within
260 the current healthcare landscape.

261 **Study Sample**

262 Qualitative Evaluation

263 For semi-structured in-depth interviews, at least two participants representing each of the
264 five implementation sites and the Ministry of Health will be purposefully sampled. They will
265 include decision-makers who are higher-level administrators or clinicians who have the authority
266 to make policy and implementation decisions. It will also include individuals who are familiar with
267 the hospital's overall frailty strategy, and those who led the development and implementation of
268 the programme.

269 We will conduct a series of focus group discussions where multiple stakeholders are
270 identified through purposive sampling. First, we will conduct focus group discussions with
271 members of the core implementation team at each of the five sites— defined as individuals with
272 time funded through the programme who have been providing services in the GSH for at least six
273 months. They may include doctors, nurses, allied health professionals, and administrative or
274 operations personnel. Second, for each site, at least five members of the staff from partner

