275 organisations including primary care clinics, and aged care facilities will be identified for another
276 round of focus group discussions. They may include the heads of doctors, nurses and
277 administrative staff who provided services within the new programme for at least six months.
278 Third, we aim to identify at least ten participants who receive care under the new model for at least
279 three months for the last round of focus group discussions. They must be able to take part in
280 conversation for at least 60 minutes. For individuals who do not have the capacity to participate,
281 his/her primary caregiver is eligible for participation.

282 We will conduct participant observations to better understand the processes involved by
283 shadowing 3 to 5 members of the staff over the course of one week per site to account for day-to-
284 day variations and job role differences.

285 Quantitative Evaluation

286 First, quality indicators will be developed to measure the processes of care for all individuals
287 enrolled into each programme. The relevant sub-populations accessing each care component will
288 form the denominator for computation of the indicators.

289 Second, we aim to recruit patients enrolled in the new programme. A target sample of 300
290 participants per site will be recruited. The sample was calculated based on the Barthel Index (100
291 points) – a scale to assess physical functioning, the key health outcome expected to improve as a
292 result of participation in the GSH. We computed the sample size for each participating site using
293 the dependent t-test to detect a small effect size of 0.2 (based on $\beta = .80$, $\alpha = .05$) (45). The result
294 was a minimum sample size of 156 per participating site. Allowing 20% rejection rate at the first
295 instance and a subsequent attrition rate of 30%, we would need to approach 300 individuals at the
296 first instance.

297 (Insert) Figure 1 Study sample for quantitative evaluation

298 Third, propensity score matching will be used to match programme enrollees and a
299 constructed comparator group. Both groups will be matched based on their probability of being
300 enrolled into the programme conditional on baseline covariates (46). The propensity score can be
301 used to mitigate selection bias in a non-randomised study. All programme enrollees will be
302 included as cases. Data on comparators will be derived from a Ministry of Health dataset

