420 the progress of the programme. Baseline characteristics will be described with mean and SD for
421 continuous variables, and number and percentage for categorical variables.

422 For survey-collected outcomes, Generalised Linear Models (GLM) will be used to allow us
423 to make inferences about the population when accounting for the within-subject correlation.

424 A propensity score conditional upon observed covariates will be computed for all cases
425 (Figure 1). Variables will include sociodemographic information, disease burden measured by the
426 Charlson Comorbidity Index (55), and physical functional status. We will match 2 comparators to
427 1 case using nearest-neighbour matching. In a Monte Carlo simulation, the mean squared error for
428 a 2:1 match was minimised in 84 percent of the simulations compared with 68 percent for a 1:1
429 match (56). Nearest neighbour matching based on a calliper of 0.01 of the standard deviation of
430 the propensity score will be used (46, 57). Only cases and comparators with propensity scores

431 falling within a common support region range will be included in the analysis to ensure
432 comparability of the two groups.

433 In the multivariable regression analysis of count data, Poisson distribution or Negative
434 Binomial distribution (variance greater than the mean) will be used. Negative Binomial regression
435 can be used for over-dispersed count data when the conditional variance exceeds the conditional
436 mean. GLM will be used for modelling non-normally distributed continuous data such as length
437 of stay and healthcare cost. The results will be presented as incidence-rate ratios (IRRs). All
438 analyses will be performed using Stata/SE 16.1(58), with the level of significance set at 5%.

439 Integration of qualitative and quantitative data

440 Qualitative and quantitative data are collected concurrently and analysed separately. In the
441 final interpretation of the data, we will bring together and triangulate the results from the various
442 coordinated parts (59). Findings from each component of a study will be listed to allow the
443 evaluation team to look for convergence in findings, offer complementary information on the same
444 issues and to highlight discrepancies (60). Findings from interviews, focus group discussions and
445 participant observations will be used to contextualise quantitative process indicators and for

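### Prior healthcare use and cost are not among the listed propensity-score variables or named in the outcome models, so the matched comparison may be biased in either direction

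*Combined protocol and SAP*

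**What the plan says.** The Data Analysis section (Quantitative evaluation) opens this component with "A propensity score conditional upon observed covariates will be computed for all cases". It then gives the variables: "Variables will include sociodemographic information, disease burden measured by the" "Charlson Comorbidity Index (55), and physical functional status. We will match 2 comparators to" one case. The calliper sentence reads "Nearest neighbour matching based on a calliper of 0.01 of the standard deviation of" the propensity score.

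The outcome models follow: "In the multivariable regression analysis of count data, Poisson distribution or Negative" Binomial, with GLM for length of stay and cost. They are called multivariable, but no covariate, period term or group-by-period term is named.

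Elsewhere the plan says:

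- Evaluation Design, Quantitative Evaluation: "Third, a retrospective pre-post, matched-groups design will be implemented to compare" use and cost. No pre or post window is defined.
- Table 2, objective 3: "To assess the use of healthcare services and costs between participants and non-participants for each programme". The text after the table leaves four of the five sites in this objective.
- Table 1: the hospital emergency department is the primary referral source at the Changi site, the only site so listed.
- Study Sample: all enrollees are cases. Comparators come from a Ministry of Health dataset on community-dwelling older adults, gathered during government outreach.
- Study Procedure: the linked dataset is to hold use and system cost across public institutions. No look-back period is stated, and the identifier step is described for enrollees only.

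**The concern.** A person's recent use of care usually predicts later use and cost, and it can also lead to referral. If it is left out of the match, two people with the same age, Charlson index and function can still have different expected use. At the Changi site the usual route into the programme is itself a use event, while nothing says that comparators were picked up through a care episode.

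This is the only quantitative component with a comparator group. It tests the hypothesis that emergency hospitalisation and overall cost may fall, and the Strengths and limitations section relies on the match for the validity of those conclusions. That section concedes unmeasured confounding in general terms. Prior use is different, because the team may well hold the records to measure it.

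The missing contrast matters as much as the missing covariate. A post-period comparison and a group-by-period comparison can fall on opposite sides of 1 for the same data. If the choice is left until outcomes are seen, so is the direction of the finding.

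**Working it through.** The plan gives no sample size, event rate or effect size for the matched comparison, so there is no figure to reproduce. All rates below are assumed, and the true incidence-rate ratio (IRR) is 1.

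**Illustration: enrolment triggered by a visit**

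Inputs (assumed): mean emergency visits per person-year m = 0.5 or 1.0; gamma-Poisson counts with dispersion k = 0.1, 0.5 or 1.0 left after matching; a share p = 0.25 of enrolments triggered by at least one visit in the prior 12 months, the rest unrelated to prior use.

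1. Probability of no visit in a year: P0 = (1 + km)^(-1/k).
2. Later rate of triggered enrollees relative to comparators: r = [1 - P0/(1 + km)] / (1 - P0).
3. Post-only IRR = 1 + p(r - 1).
4. Pre-period ratio, referring visit counted = 1 + p[1/(1 - P0) - 1].
5. Group-by-period ratio = step 3 / step 4.

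| m | k | P0 | r | Post-only IRR | Pre ratio | Group-by-period |
|---|---|---|---|---|---|---|
| 0.5 | 0.1 | 0.614 | 1.076 | 1.019 | 1.398 | 0.729 |
| 0.5 | 0.5 | 0.640 | 1.356 | 1.089 | 1.444 | 0.754 |
| 0.5 | 1.0 | 0.667 | 1.667 | 1.167 | 1.500 | 0.778 |
| 1.0 | 0.1 | 0.386 | 1.057 | 1.014 | 1.157 | 0.877 |
| 1.0 | 0.5 | 0.444 | 1.267 | 1.067 | 1.200 | 0.889 |
| 1.0 | 1.0 | 0.500 | 1.500 | 1.125 | 1.250 | 0.900 |

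The post-only contrast reads 1.01-1.17, against the programme. The group-by-period contrast reads 0.73-0.90, in its favour, through regression to the mean. At the lowest dispersion the post-only bias is only 1-2%.

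**How far does adjusting for the prior count help?**

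Suppose referral follows a stable underlying rate. Assume a comparator mean of 0.5, an enrollee mean mu of 0.55-1.0, and the same gamma shape a (1 or 10) in both groups.

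- Without the prior count: mu/0.5 = 1.10 to 2.00.
- Given the same prior count: (a/0.5 + 1)/(a/mu + 1). For a = 1 this is 3/2.818 = 1.06 and 3/2 = 1.50; for a = 10 it is 21/19.18 = 1.09 and 21/11 = 1.91. The range is 1.06-1.91.
- Group-by-period: (mu/0.5)/(mu/0.5) = 1.00.

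**A second model as a check**

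This is a Poisson simulation with 200,000 people per scenario, in which regression on two measured covariates stands in for matching. The stable and transient parts of use each have a log-scale SD of 0.7.

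| Selection on | Post-only | Group-by-period | Adjusted for prior count |
|---|---|---|---|
| nothing | 1.02 | 1.01 | 1.01 |
| stable use | 1.29 | 1.02 | 1.21 |
| transient spike | 1.02 | 0.78 | 0.95 |
| both | 1.27 | 0.77 | 1.11 |
| lower stable use | 0.86 | 0.99 | 0.89 |

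The first row indicates simulation noise of about 0.02. Each contrast is close to right under one mechanism and wrong under another.

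**The case against.** The strongest defence is that the text is open rather than wrong. The variable list is introduced by a word that need not be exhaustive, and the Study Sample section says cases are to be "enrolled into the programme conditional on baseline covariates (46). The propensity score can be" used against selection bias, without limiting which covariates count. The models are multivariable, the design is labelled pre-post, and Figure 1 is not visible in the copy reviewed. A reader might infer that the plan excludes prior use. The documents do not support that: prior use is unlisted, not ruled out. What remains is that the baseline values of the outcomes are missing from the only list given, and that the pre-post label is never carried into the matching or the models.

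A second objection concerns the remedy. It is tempting to make the adjusted post-period contrast the main one and treat group-by-period as secondary. The working does not support that ranking: under stable-rate selection the adjusted estimate can still read 1.91 with no effect, while group-by-period reads 1.00. Under a transient spike the order reverses, and adjustment may overshoot slightly below 1. The documents do not give the referral mechanism.

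Third, the illustration does not bound the problem. The emergency department is only the primary source at one of four sites. Results also depend on whether every visit or only some visits lead to referral, and on how the referring visit is counted. This objection stands. No figure is offered for cost.

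**Conclusion.** The point holds as an improvement that should be made, at medium confidence. The listed score variables omit prior use and cost, no pre-period term is named in the models, and the contrast is not stated. Imbalance in prior use is plausible, most clearly at the emergency-referred site; that is an inference from Table 1 and the comparator source, not a stated fact.

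The direction of bias depends on the referral mechanism and on the contrast, and its size cannot be derived from the documents. The 1.01-1.17 and 0.73-0.90 ranges rest wholly on the assumed visit rates, dispersion and quarter share of triggered enrolments. A reader might conclude that the comparison will understate, or will overstate, the programme's effect; neither follows.

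**What to change.** 1. Give each candidate comparator an index date before scoring, for example by allocating candidates to enrolment-quarter strata and matching within them. Define the pre and post windows, including how the referring visit is counted.
2. Add 12-month pre-index emergency, inpatient, specialist and primary-care use and total cost to the propensity score. Report balance on them and the number of unmatched cases, by site.
3. Enter the pre-period value of each outcome as a covariate in its count or GLM model.
4. Name the main contrast before outcomes are analysed. Report both the adjusted post-period and the group-by-period estimates, without claiming that either is better in general.

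These steps reduce the bias but need not remove it, and the report should say so.

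The cost is protocol wording, extra programming and a look-back in records that the plan already intends to link; no new data are collected from patients. The sponsor must first confirm that look-back records exist for comparators. Some matches will probably be lost under the 0.01 SD calliper and the common-support rule, most likely at the emergency-referred site. How many depends on the size of the comparator pool, which the documents do not give.
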